## 7.2.2. Clinical Laboratory Evaluations

Clinical laboratory evaluations (clinical chemistry panel [fasted at least 8 hours; at EOT or ET, subjects are not required to be fasted prior to clinical laboratory evaluations], coagulation parameters, hematology panel, TSH [Screening only], HbA1c [Screening only], eGFR [Screening and Check-in (Day -1)] and UA) will be collected at the timepoints specified in Appendix 4.

Screens for HCV antibody, HbsAg, HBV core antibody, and HIV antibody will be performed at Screening.

Testing for COVID-19 via PCR or equivalent will be performed at the timepoints specified in Appendix 4. Testing for COVID-19 may also be conducted periodically during the subject's CRU confinement, at the discretion of the Investigator (or designee). Further details

regarding COVID-19 testing (including procedures for subjects who test positive at any time

A urine drug screen for selected drugs of abuse (including cotinine and alcohol) will be performed at Screening and repeated at Check-in (Day -1) for all subjects. A serum qualitative pregnancy test (female subjects only [serum quantitative may be used for confirmation if needed]) and an FSH test (post-menopausal female subjects only) will be performed at the timepoints specified in Appendix 4.

throughout CRU confinement) are specified in a separate document.

The number of blood samples and total blood volume required for clinical laboratory evaluations are presented in Appendix 3. A list of the specific evaluations is in Appendix 2.

#### 7.2.3. Vital Signs

Vital sign measurements (including oral temperature, respiratory rate, and supine BP, oxygen saturation and pulse rate) will be obtained at the timepoints specified in Appendix 4.

Blood pressure and pulse rate measurements should be performed using the same arm for each reading and measurements should be taken after the subject has been resting in the supine position for at least 5 minutes.

When vital sign measurements are scheduled at the same time as blood draws, the blood draws will be obtained at the scheduled timepoint, and the vital sign measurements will be obtained prior to and as close as possible to the scheduled blood draw.

## 7.2.4. 12-lead Electrocardiogram

A 12-lead ECG (including heart rate, PR, RR, QRS, and QT interval parameters) will be obtained after the subject has been resting for at least 10 minutes in the supine position at the timepoints specified in Appendix 4. The QT interval will be corrected for heart rate by Fridericia's (QTcF = QT/[RR] $^{1/3}$ ) formula.

When 12-lead ECGs are scheduled at the same time as blood draws, the blood draws will be obtained at the scheduled timepoint, and the 12-lead ECGs will be obtained prior to and as close as possible to the scheduled blood draw.

#### 7.2.5. Physical Examination

A complete or abbreviated physical examination will be performed at the timepoints specified in Appendix 4. Complete physical examinations will evaluate general appearance and the following body systems/organs: dermatological; head and eyes; ears, nose, mouth, and throat; pulmonary; cardiovascular; abdominal; lymphatic; musculoskeletal/extremities; and neurological. Weight and height will be reported (height only reported during Screening). Abbreviated physical examinations will evaluate general appearance and the following body systems/organs: dermatological; pulmonary; cardiovascular; abdominal; and neurological.

#### 8. SAMPLE SIZE AND DATA ANALYSIS

# 8.1. Determination of Sample Size

Up to sixteen healthy adult male and female subjects (women of non-childbearing potential only) will be enrolled. The sample size chosen for this study was selected without statistical considerations, but is consistent with previous studies of a similar design. Up to sixteen subjects are anticipated to be sufficient to provide a reliable estimate of the magnitude and variability of the interaction. Replacement subjects may be enrolled only if deemed necessary by the Sponsor. Every attempt will be made to enroll at least 4 subjects of each sex in the study.

#### 8.2. Analysis Populations

## **8.2.1.** Study Populations

The **PK Population** will consist of all subjects who have received a dose of LOXO-305, have at least 1 quantifiable plasma concentration, and for whom at least 1 PK parameter can be computed. A subject may be excluded from the PK summary statistics and statistical analysis if the subject has an AE of vomiting that occurs at or before 2 times median tmax for the analyte being evaluated. The impact of protocol deviations on PK population will be evaluated on a case-by-case basis.

The **Safety Population** will consist of all subjects who have received at least 1 dose of study drug (repaglinide and/or LOXO-305). Subjects will be classified into groups based on actual treatment received.

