From AE data reported following LOXO-305 administration in 10 healthy volunteers in the LOXO-BTK-20014 study, all TEAEs (headache, nausea, and vomiting) were Grade 1 in severity and considered related to LOXO-305. All 3 events were reported by 1 subject and resolved within 1 to 1.5 days (data on file at the time of protocol development). From preliminary AE data reported following LOXO-305 administration in healthy volunteers in the LOXO-BTK-20006 study, all TEAEs (intermittent belching, bloating, insect bite, aphthous ulcer, nausea, intermittent diarrhea (x2), muscle twitch) were Grade 1 in severity and bloating, intermittent diarrhea and intermittent belching were considered related to LOXO-305. All 7 AEs were reported by 3 subjects and all events resolved prior to EOT; data on file at the time of protocol development). From preliminary AE data reported following LOXO-305 administration in healthy volunteers in Cohort 1 of the LOXO-BTK-20017 study, there was 1 TEAE (headache) observed in the 300 mg LOXO-305 cohort which was Grade 1 in severity and considered related to LOXO-305. The event resolved within 2 hours (data on file at the time of protocol development).

There is a potential risk that multiple doses of LOXO-305 may lead to decreases in white blood cells including neutrophils, lymphocytes, monocytes, and eosinophils. Therefore, to mitigate any potential immunosuppressive risks during the ongoing SARS-CoV-2 (COVID-19) pandemic, subjects will remain in the Clinical Research Unit (CRU) for 100 hours postdose (approximately 5 half-lives) which is Day 16 to allow for LOXO-305 elimination. In addition, subject's hematology laboratory results will be reviewed prior to discharge from the CRU. More information about the known and expected benefits, risks, and reasonably anticipated AEs associated with LOXO-305 may be found in the IB. 

The dosing regimen of the oral dose of repaglinide in the current study is consistent with use in DDI studies. Hypoglycemia is a possible side effect; however, subjects will be given breakfast, lunch, dinner, and an optional snack after dinner on the day before dosing and will have a standardized light breakfast (Table 4)15 minutes postdose to mitigate any potential side effects. The potential risk of participating in this study and receiving this drug is well managed by the study set-up and considered negligible.

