#### 8.3.2. Statistical Methodology

A mixed model will be performed to evaluate the effects of multiple-dose administration of LOXO-305 on repaglinide. The mixed effect model will include treatment as a fixed effect and subject as a random effect. The analysis will be performed on the In-transformed PK parameters (AUC0-t, AUC0-inf, and Cmax) and will include calculation of least squared (LS) means and the difference between treatment LS means, as well as their corresponding 90% confidence intervals (CIs). The geometric mean ratios and their 90% CIs of the PK parameter for each treatment comparison will be constructed using the exponentiation of the difference and the CIs from the mixed effect model. The primary comparison for this study is 0.5 mg repaglinide + multiple-dose of LOXO-305 versus 0.5 mg repaglinide.

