#### 7.3. Pharmacokinetic Population

The PK Population will include all subjects who received a dose of LOXO-305, have at least 1 quantifiable plasma concentration, and for whom at least 1 PK parameter can be computed. A subject may be excluded from the PK summary statistics and statistical analysis if the subject has an AE of vomiting that occurs at or before 2 times median  $t_{max}$  for the analyte being evaluated. The impact of protocol deviations on PK population will be evaluated on a case-by-case basis.

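### The PK Population requires a LOXO-305 dose, so whether a Day 1-only repaglinide profile enters the reference depends on a dose given after it was collected (minor)

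*Protocol*

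**What the plan says.** Protocol Section 8.2.1 defines the PK Population as "all subjects who have received a dose of LOXO-305, have at least 1 quantifiable plasma concentration". It adds a third condition, one or more computable PK parameters. SAP Section 7.3 carries the same rule: "The PK Population will include all subjects who received a dose of LOXO-305, have at least 1 quantifiable plasma concentration", again with at least one computable parameter. Neither document ties the concentration or the parameter to an analyte or a period, so Day 1 repaglinide data satisfy both of those conditions. Only the LOXO-305 condition cannot be met on Day 1.

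The surrounding text gives the rule its effect:

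- Protocol Section 3.1 gives repaglinide alone on Day 1 and the first LOXO-305 dose on Day 2.
- SAP Section 8.5.3.1 makes Day 1 the reference and Day 12 the test treatment for AUC0-t, AUC0-inf and Cmax.
- SAP Section 8.1 confines summaries and analyses to members of the relevant population.
- Protocol Section 8.3.2 specifies the model: "The mixed effect model will include treatment as a fixed effect and subject as a random effect". Neither document adds a completers-only rule.
- The Safety Population, also in Protocol Section 8.2.1, is wider: "all subjects who have received at least 1 dose of study drug (repaglinide and/or LOXO-305").

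**The concern.** The reference measurement is complete, or nearly so, before the entry condition can be met. Membership of the reference group therefore turns on a later event that carries no information about the Day 1 repaglinide profile. Two subjects with identical repaglinide data can be treated differently.

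Two results could be affected. The first is the descriptive repaglinide-alone summary, which reports primary endpoints. The second is the Day 12/Day 1 ratio. If the subjects who stop early tend to have high Day 1 values, those who remain have Day 1 values that are low partly by chance. Their Day 12 values drift back towards the mean, and the ratio is pushed up. A random-subject model can use one-period subjects to offset this, but the definition withholds some of them.

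**Working it through.** **Applying the rule.** The plan states no power, SD or effect size, so there is no figure of its own to reproduce. The first check is logical.

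| | LOXO-305 dose | Quantifiable concentration | Computable parameter | PK Population |
|---|---|---|---|---|
| Subject A: Day 1 repaglinide, stops before Day 2 dose | no | yes | yes | out |
| Subject B: same Day 1 data, one LOXO-305 dose, then stops | yes | yes | yes | in |

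Neither has Day 12 data, so their repaglinide information is the same.

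**Can another clause re-admit A?** The vomiting clause only excludes. The remaining clause reads "The impact of protocol deviations on PK population will be evaluated on a case-by-case basis"; it gives no stated basis for adding someone who fails the definition, and withdrawing before Day 2 need not be a deviation. Replacement under Protocol Section 4.5 is at the sponsor's discretion and does not restore A's profile.

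**Inputs for sizing.** From the documents: up to 16 subjects, a random-intercept model on the ln scale, and a 90% CI. Assumed, because the documents give none of these: within- and between-subject variability, the number who stop, and any link between stopping and exposure.

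**Formulas.** Let w² and b² be the within- and between-subject ln variances, k = w²/(w²+b²), n the number of complete pairs and m the number of Day 1-only subjects. With variances treated as known:

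- Pairs only: Var(ln ratio) = 2w²/n.
- Day 1-only subjects kept: Var = (2w²/n) × [1 − k·m/(2(n+m))].
- One kept subject lying d above the paired Day 1 mean moves the ln ratio by −k·d/(n+1).
- If the pairs' mean ln Day 1 value is too low by β through selection on Day 1, the pairs-only ln ratio is too high by k·β.

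**Precision.** Take within-subject CV 30%, between-subject CV 50%, n = 15, m = 1. Then w² = ln 1.09 = 0.0862, b² = ln 1.25 = 0.2231 and k = 0.279. The SE ratio is √(1 − 0.279/32) = 0.9956. The 90% half-width goes from exp(1.761 × 0.1072) = 1.208-fold to 1.207-fold. Over within-subject CV 20–40% and between-subject CV 30–70%, the SE falls by 0.1–1.0% for one such subject and by 0.6–4.0% for four (12 pairs + 4). One kept subject at twice the reference mean multiplies the ratio by 0.973 to 0.996.

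**Bias, extreme case.** Assume b = 0.5, w = 0.2 or 0.3, a true ratio of 1.20, and that the highest one or two Day 1 values of 16 are always the ones lost. The expected two largest of 16 standard normal values are 1.766 and 1.285. So β = SD × 1.766/15 for one lost, or SD × 3.051/14 for two, with SD = √(b²+w²).

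| w | Lost | SD | k | β | Day 1 geometric mean, kept/true | Ratio = 1.20·exp(kβ) |
|---|---|---|---|---|---|---|
| 0.2 | 1 | 0.539 | 0.138 | 0.063 | 0.94 | 1.210 |
| 0.2 | 2 | 0.539 | 0.138 | 0.117 | 0.89 | 1.220 |
| 0.3 | 1 | 0.583 | 0.265 | 0.069 | 0.93 | 1.222 |
| 0.3 | 2 | 0.583 | 0.265 | 0.127 | 0.88 | 1.241 |

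Simulation agrees: 1.210–1.226 with one lost and 1.216–1.243 with two. With the Day 1-only subjects kept, the REML random-intercept estimate averages 1.195–1.202.

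**Bias, weaker link.** If stopping correlates only 0.5 with Day 1 exposure, β halves. Simulation gives 1.206–1.211 (one lost) and 1.208–1.218 (two lost), about 0.5–1.5% too high.

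**Bias, no link.** If stopping is unrelated to exposure, both approaches average 1.20 with the same SD.

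**Yardstick.** With w = 0.2–0.3 and 14–15 pairs, the 90% CI half-width is 1.14- to 1.22-fold.

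**The case against.** The strongest reply is that this changes almost nothing. The primary result is a within-subject ratio, and a subject without Day 12 data adds very little to it. The rule is pre-specified, identical in both documents and coherent with a question about the effect of LOXO-305. Nothing is hidden either: SAP Sections 8.1 and 8.5.3 list all captured data and all PK concentrations and parameters, and SAP Section 1 permits identified supplementary analyses. All of this stands and sets the size of the point. It does not explain why Subject B's profile belongs in the reference and Subject A's does not.

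A reader might infer something stronger: that the expected reason to stop before Day 2 is a reaction to repaglinide, that such reactions mark high exposure, and that the primary ratio is therefore biased upward. The documents do not support this. Protocol Section 1.6 says only "Hypoglycemia is a possible side effect", describes meals meant to mitigate it and rates the risk as negligible. Section 4.6 gives other reasons for leaving. No dropout rate and no exposure–tolerability relation is stated. Nor should the 6–12% figure be read as bias in the primary ratio: it concerns the descriptive Day 1 geometric mean in the extreme case.

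The Day 1 sampling times are redacted, so it cannot be confirmed that a subject who stops before the Day 2 dose has a full profile. The asymmetry needs only one computable parameter, such as Cmax, so this limits the point without removing it.

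**Conclusion.** The inconsistency is real and follows from the wording of both documents; no clause repairs it. Severity is minor. It arises only if someone stops between the Day 1 and Day 2 doses.

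- Stopping unrelated to exposure: no bias, and an SE change of 1% or less for one subject.
- Stopping assumed to track high Day 1 exposure: the ratio is about 0.5–3% too high for one or two subjects, at between-subject ln SD 0.5 and within-subject ln SD 0.2–0.3. This is small beside a CI half-width of about 14–22%.
- Upper end: in the extreme case with two lost and within-subject ln SD 0.4, kβ = 0.390 × 0.1395 = 0.054, or about 5.6%. The interval is wider there too, about 1.31-fold.

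Keeping the Day 1-only subjects corrects the bias only if stopping depends on the observed Day 1 values and the random-intercept model holds.

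**What to change.** In Protocol Section 8.2.1 and SAP Section 7.3, replace the LOXO-305 dose condition with receipt of at least one dose of either study drug, as the Safety Population already has it. Apply the quantifiable-concentration and PK-parameter conditions by analyte and treatment, so that every valid Day 1 repaglinide profile enters the repaglinide-alone summary and the planned mixed model. Add the paired-subjects-only ratio as a sensitivity line. Record the change in SAP Section 10, which now reports none, and settle it before database lock.

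The cost is one sentence in the SAP, which by its Section 1 supersedes the protocol's statistical text, and one in the protocol if it is amended. The small downside is that the Day 1 n may exceed the Day 12 n in the tables, which a footnote can explain.

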## 8.3. Pharmacokinetic Analysis

Blood samples for plasma concentration analysis will be collected for the following:

- Repaglinide:
  - Serial PK blood samples CC
     .
- LOXO-305:
  - Serial PK blood samples CC
  - Blood samples CCI

Whenever possible, the following PK parameters will be calculated for each subject, based on the plasma concentrations of repaglinide following single dose administration (as appropriate):

AUC from hour 0 to the last measurable concentration, calculated using the linear trapezoidal rule for increasing and decreasing concentrations

AUC from hour 0 extrapolated to infinity, calculated using the formula:

 $AUC_{0-inf} = AUC_{0-inf} = AUC_{0-t} + \frac{C_t}{\lambda_z}$ 

where  $C_t$  is the last measurable concentration and  $\lambda_Z$  is the apparent

terminal elimination rate constant.

%AUCextrap percentage extrapolation for AUC0-inf

Cmax maximum observed plasma concentration

tmax time to maximum observed plasma concentration

apparent terminal elimination rate constant, where  $\lambda_Z$  is the magnitude

 $\lambda z$  of the slope of the linear regression of the log concentration versus time

profile during the terminal phase

CL/F apparent systemic clearance

apparent plasma terminal elimination half-life (whenever possible),  $t_{1/2}$ 

where  $t_{1/2} = \ln(2)/\lambda_Z$ 

Vz/F apparent volume of distribution during the terminal phase

Wherever possible, the following PK parameters will be calculated for each subject, based on the plasma concentrations of LOXO-305 following multiple dose administration (as appropriate):

AUC 0-t	AUC from hour 0 to the last measurable concentration, calculated using the linear trapezoidal rule for increasing and decreasing concentrations
$AUC_{tau} \\$	area under the concentration-time curve during a dosing interval
CL,ss/F	apparent systemic plasma clearance after oral (extravascular) administration, calculated as Dose/AUC tau (Day 12)
$C_{\text{max}}$	maximum observed plasma concentration at steady state
$C_{trough}$	concentration observed at the end of the dosing interval
$t_{max}$	time to reach $C_{max}$ . If the maximum value occurs at more than one timepoint, $t_{max}$ is defined as the first timepoint with this value.

Pharmacokinetic calculations will be performed using commercial software such as Phoenix™ WinNonlin® Version 8.1 or higher (Certara USA Inc.).

The  $\lambda z$  and  $t_{1/2}$  will be calculated by linear least squares regression analysis using the maximum number of points in the terminal log linear phase (eg, 3 or more non-zero plasma concentrations).

Other parameters may be added, as appropriate. Final PK parameters reported will be detailed in the Statistical Analysis Plan (SAP).

Pharmacokinetic analysis will use actual times as recorded on the eCRF. All statistical analysis will be performed using SAS® Version 9.4 or greater. More details on the analyses will be included in the SAP.

## 8.3.1. Descriptive Analysis

Plasma concentrations and PK parameters will be summarized with descriptive statistics (number, arithmetic mean, standard deviation, coefficient of variation [CV%], geometric mean, geometric CV%, median, minimum, and maximum).

Individual and mean plasma concentration-time curves (both linear and log linear) will be included in the final report.

#### 8.3.2. Statistical Methodology

A mixed model will be performed to evaluate the effects of multiple-dose administration of LOXO-305 on repaglinide. The mixed effect model will include treatment as a fixed effect and subject as a random effect. The analysis will be performed on the In-transformed PK parameters (AUC0-t, AUC0-inf, and Cmax) and will include calculation of least squared (LS) means and the difference between treatment LS means, as well as their corresponding 90% confidence intervals (CIs). The geometric mean ratios and their 90% CIs of the PK parameter for each treatment comparison will be constructed using the exponentiation of the difference and the CIs from the mixed effect model. The primary comparison for this study is 0.5 mg repaglinide + multiple-dose of LOXO-305 versus 0.5 mg repaglinide.

## 8.4. Safety Analysis

All safety assessments, including AEs and SAEs, vital sign measurements, clinical laboratory results, physical examination results, concomitant medications, and 12-lead ECGs, will be tabulated and summarized where possible, using descriptive methodology, as needed, by treatment and timepoint. Unless otherwise specified, baseline value is defined as the last non-missing measurement before administration of study drug on Day 1. No formal statistical analyses are planned for the safety data. All safety data will be listed by subject.

Concomitant medications will be coded using the World Health Organization (WHO) Drug Dictionary (WHO Drug Global B3, September 2019) and AEs will be coded using MedDRA Version 22.1 (or higher). The incidence of AEs will be presented by severity and by relationship to study drug as determined by the Investigator ([or designee], Appendix 1 for AE reporting). All TEAEs will be summarized by system organ class (SOC) and preferred term (PT).

#### 8.5. Data Handling and Record Keeping

Any changes to information in the trial progress notes and other source documents will be initialed and dated on the day the change is made by a CRU staff member authorized to make the change. Changes will be made by striking a single line through erroneous data and clearly entering the correct data (eg, wrong data right data). If the reason for the change is not apparent, a brief explanation for the change will be written adjacent to the change by the clinician.

The Data Management Plan will be approved by the Sponsor.

Data will be validated during data entry by the CRU and verified by the Study Monitor. Data will then be reviewed by the data management group to resolve any outstanding issues. Listings will be generated after the database is cleaned by data management and will be reviewed by the Covance scientific team. The eCRF and ancillary data will be converted into final SAS® datasets following Study Data Tabulation Model or client-provided specifications. The final datasets structure will be verified using Web Submission Data Manager®, while the dataset content will be peer reviewed by an independent programmer.

The tables, figures, and listings (TFLs) will be programmed per the final SAP. All TFLs will be peer reviewed by an independent programmer. In addition, draft TFLs will be reviewed by the Covance scientific team during the dry run and data review meetings.

The peer review will be performed by independent programmers following the quality control process and programming checklists.

